## 7.2. Determination of Sample Size

The CGM data collected in this addendum will be for exploratory purposes; therefore, the sample size is not based on power consideration. Assuming 25% dropout rate, 27 subjects in each treatment arm (54 total) are needed to have 20 completers in each treatment arm (40 total).

## 7.3. Analytic Variables

A third party organization (TPO) will collect and compile the CGM data. Besides the CGM raw data, the TPO will also provide the analytic variables for each patient as follows:

- daily SD of the CGM glucose measures
- daily amplitude of glycemic excursion (MAGE) index and continuous overall net glycemic action (CONGA)
- daily AUC and percentage of time when glucose measures are:
  - $\leq 70$  mg/dL
  - $\leq 50$  mg/dL
  - $\geq 180$  mg/dL
  - $\leq 70$  mg/dL during the nocturnal period between midnight and 0600 hours
  - $\leq 50$  mg/dL during the nocturnal period between midnight and 0600 hours
  - $> 70$  mg/dL to  $\leq 120$  mg/dL
- daily LBGI, HBGI, and the combined BG risk index (sum of the LBGI and HBGI) during the nocturnal period (defined as midnight to 0600 hours) and during a 24-hour period
- daily AUC between bolus doses at breakfast and lunch and daily AUC between bolus doses at lunch and dinner, respectively
- daily AUC for 4 hours after the start of each meal

MAGE is the mean of the differences between consecutive peaks and nadirs in BG, provided that the absolute value of difference was greater than the SD (Service et al. 1970). CONGA is the SD of the difference between the current and previous observations and measures the overall intra-day variation of glucose recorded by CGM (McDonnell et al. 2005).

The LBGI (Kovatchev et al. 2005) has been developed to quantitate both frequency and severity of hypoglycemia. The LBGI has been validated as a predictor of severe hypoglycemia (Kovatchev et al. 2003; Kovatchev et al. 1998), which is a SAE and could result in coma or death if unrecognized and untreated. The HBGI quantifies both frequency and severity of hyperglycemia (Kovatchev et al. 2005) and has been related to HbA1c and risk for hyperglycemia (Kovatchev et al. 2003). Additionally, the LBGI and HBGI both have a high sensitivity to changes in glycemic profiles and control (Kovatchev et al. 2002). The LBGI and HBGI will be derived values.

## 7.4. A Priori Statistical Methods

Baseline characteristics will be summarized by treatment arm. Means will be analyzed using an analysis of variance model. Proportions will be analyzed using Fisher's exact test.

The primary objective measure is mean daily SD calculated as the mean of the optimal values for each visit. An MMRM model will be used to analyze the actual measurements and change from baseline of the continuous dependent variables. The model will include fixed effects such as treatment, weeks on treatment (considered as categorical variable), the interaction between treatment and weeks, and the stratification factors. Subject will be considered as a random effect. The corresponding baseline values will be included as a covariate.

For the MMRM model, the Kenward-Roger approximation will be used to estimate denominator degrees of freedom. An unstructured covariance matrix will be used to model the within-subject errors. If the unstructured covariance configuration results in a lack of convergence, then the following variance-covariance matrix will be used (in order) until one converges:

Heterogeneous Toeplitz; Heterogeneous First Order Autoregressive; Heterogeneous Compound Symmetry; Toeplitz; First Order Autoregressive; Compound Symmetry. If all variance-covariance matrices selected fail to converge, Variance Components will be used as the next attempt at convergence.

If the model still does not converge after changing to different covariance structures, then the stratification factors will be removed from the model. If the model still does not converge, then an ANCOVA analysis which only includes baseline and the 26-week values will be performed.

The similar variable calculation method and MMRM approach will be used for all other secondary objectives. Model specifications, such as fixed effects, covariates, and repeated measurement structures need to be carefully adjusted according to the specific objectives and measurements. For Secondary Objective 4, only those subjects assigned to CSII arm will be analyzed; therefore, the treatment effect and its interactions with other effects will be removed from the model. For Secondary Objective 5, the interaction between optimal bolus timing (15 or 30 minutes prior to meal) and treatment will be added into the MMRM model; the interaction between optimal bolus timing and weeks will also be added. Depending on the model convergence situation, the interaction between treatment and weeks may be removed.

Other measures of variability of the interstitial glucose measurements may be analyzed as sensitivity analyses (for example, MAGE index and CONGA).

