## 7. CGM Addendum

Unless otherwise specified, all discussions in this section are within the context of the CGM addendum only. Subjects who choose to participate in Protocol Addendum IBHD(1) will sign an addendum-specific informed consent form (ICF). The commercial CGM device (Dexcom G4 Platinum) that will be used for this addendum is labeled to collect data for 7 consecutive days. These subjects will be asked to perform CGM on 3 occasions for up to 7 days per occasion as indicated in the Study Schedule. Continuous glucose monitoring should occur during the week prior to Visit 4 (Week 0), Visit 13 (Week 14), and Visit 17 (Week 26).

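### The CGM model pairs a random subject effect with an unstructured residual covariance on two post-baseline visits, which is not identifiable

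*SAP*

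**What the plan says.** SAP 7.4 describes the CGM analysis as an MMRM with treatment, categorical week, their interaction and the stratification factors as fixed effects. It then adds two covariance terms. One is a subject effect: "Subject will be considered as a random effect". The other is the residual matrix: "An unstructured covariance matrix will be used to model the within-subject errors". Degrees of freedom are by Kenward-Roger.

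Three statements fix the shape of the data:

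- SAP 7 schedules three CGM recordings, ahead of Weeks 0, 14 and 26.
- On the Week 0 value: "The corresponding baseline values will be included as a covariate".
- On the response: "The primary objective measure is mean daily SD calculated as the mean of the optimal values for each visit". I read this as one summary value per subject per visit.

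On non-convergence the residual structure changes in this order: "Heterogeneous Toeplitz; Heterogeneous First Order Autoregressive; Heterogeneous Compound Symmetry; Toeplitz; First Order Autoregressive; Compound Symmetry". After those, "Variance Components will be used as the next attempt at convergence". If that also fails, the stratification factors are dropped, and last comes an ANCOVA on the baseline and Week 26 values. Nowhere does SAP 7.4 say that the random effect is left out when a residual structure is fitted. The main-study HbA1c model in SAP 5.9 uses the same ladder and the same degrees-of-freedom method, and names no random subject effect.

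**The concern.** An unstructured residual matrix already describes all variation and correlation within a subject. A random subject effect on top of it adds a parameter about which the data carry no information. The redundancy is algebraic, so it occurs whatever the CGM data look like.

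Two things are at stake. The first is inference: Kenward-Roger uses the information matrix of the covariance parameters, and that matrix is singular here. The second is model choice: SAP 7.4 moves down its ladder whenever a fit fails to converge. A fault in the specification could therefore be taken for a difficulty with the data and lead to a more restrictive model than the data require. The plan also does not say whether a fit with a singular Hessian, or with the subject variance held at zero, counts as converged. Two programmers could report different models.

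**Working it through.** **Inputs.** From SAP 7 and 7.4: three CGM occasions, baseline as covariate, one value per visit. This leaves t = 2 responses per subject (Weeks 14 and 26) with no replication within a visit. From SAP 7.2: 27 subjects per arm, 25% dropout, 20 completers per arm. Assumed, because the documents give no CGM variances: correlation 0.5 between Weeks 14 and 26, and Week 26/Week 14 variance ratios from 0.5 to 2.

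**The plan's own figure.** 20/(1 − 0.25) = 26.67, rounded up to 27 per arm, 54 in total. This reproduces. The documents give no figure for the covariance model itself.

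**Step 1: what the data can identify.** The marginal covariance of a subject's two responses is V = R + τ²J, where R is the residual matrix, τ² the subject variance and J a 2 × 2 matrix of ones. V has t(t + 1)/2 = 3 distinct elements, or 2 if the variances are held equal.

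**Step 2: count for each structure.** Rank is that of the derivative of the elements of V with respect to the parameters. A structure is identified when rank equals the parameter count.

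| Structure for R | Parameters in R | With random effect | Rank | Identified |
|---|---|---|---|---|
| Unstructured | 3 | 4 | 3 | no |
| Heterogeneous Toeplitz | 3 | 4 | 3 | no |
| Heterogeneous AR(1) | 3 | 4 | 3 | no |
| Heterogeneous CS | 3 | 4 | 3 | no |
| Toeplitz | 2 | 3 | 2 | no |
| AR(1) | 2 | 3 | 2 | no |
| CS | 2 | 3 | 2 | no |
| Variance Components | 1 | 2 | 2 | yes |

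Without the random effect, all eight are identified. Moving baseline into the response would not rescue the first choice: at t = 3, unstructured plus a random intercept has 7 parameters and rank 6.

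**Step 3: what this does to a fit.** On one simulated data set (27 per arm, 25% missing at Week 26), τ² was fixed at several values and the unstructured R was refitted by REML.

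| τ² | R: Week 14 variance, Week 26 variance, covariance | −2 REML | Week 26 difference (SE) |
|---|---|---|---|
| 0 | 0.9918, 0.7331, 0.2759 | 89.977752 | −0.0362 (0.2753) |
| 0.2 | 0.7918, 0.5331, 0.0759 | 89.977752 | −0.0362 (0.2753) |
| 0.4 | 0.5918, 0.3331, −0.1241 | 89.977752 | −0.0362 (0.2753) |

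Whatever is added to τ² comes off every element of R, and V does not move. The ridge has an end: at τ² = 0.6 the likelihood is still the same, but R is no longer a valid covariance matrix (0.3918 × 0.1331 − 0.3241² = −0.053). Along the ridge, the Hessian for the four covariance parameters has eigenvalues 0, 63.6, 157.8 and 212.8, so it is singular.

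**Step 4: if the ladder runs to Variance Components.** With the random effect kept, R = σ²I gives V = σ²I + τ²J. This is compound symmetry: correlation is kept and the two visits share one variance. The table shows 150 simulated trials per ratio.

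| Week 26/Week 14 variance | Mean SE, unstructured | Mean SE, Variance Components + random effect | Ratio | Empirical SD of the latter estimate |
|---|---|---|---|---|
| 0.5 | 0.2157 | 0.2718 | 1.26 | 0.2276 |
| 0.67 | 0.2534 | 0.2881 | 1.14 | 0.2724 |
| 1 | 0.3088 | 0.3098 | 1.00 | 0.2830 |
| 1.5 | 0.3731 | 0.3366 | 0.90 | 0.4100 |
| 2 | 0.4312 | 0.3689 | 0.86 | 0.4183 |

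The empirical SDs carry a Monte Carlo error of about 6% (1/√(2 × 149) = 0.058). At the two ends the reported SE is too large (0.2718 against 0.2276) and too small (0.3689 against 0.4183).

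**The case against.** The strongest reply is that the sentence is loose wording. SAP 7.4 calls the model an MMRM, ties the unstructured matrix to the within-subject errors and shares its ladder with SAP 5.9. The author may have meant only that subject is the unit of repetition. That is plausible and lowers the importance. But the literal text specifies both terms, and a programmer who follows it would fit both.

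The second reply is that the redundancy is harmless to the estimate. That stands. If the software stops anywhere on the ridge or sets the subject variance to zero, the Week 26 estimate and its model-based SE are those of the plain unstructured model, as Step 3 shows. What remains is the Kenward-Roger calculation, or a convergence failure. Either depends on the software, and the documents cannot show that it would occur.

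The third reply is that little rests on the result. SAP 7.2 calls the CGM data exploratory and the sample size unpowered, and no CGM measure is among H1 to H10. That also stands.

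A reader might also infer that the fault leads on to removal of the stratification factors and then to the ANCOVA. The documents do not support this. SAP 7.4 reaches those steps only after Variance Components has failed, and that structure is identified with the random effect (2 parameters, rank 2). A failure there would have another cause. Nor does ending at Variance Components mean that Weeks 14 and 26 are treated as independent, because the random effect preserves the correlation.

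**Conclusion.** As written, the CGM model is not identifiable: 4 covariance parameters for 3 moments. The six fallback structures before Variance Components share the fault. This needs no assumption beyond two modelled visits, one value per visit and the literal reading of the sentence.

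The harm is possible, not certain, and takes one of two forms:

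- The fit converges. The Week 26 estimate is that of the plain unstructured model, but the degrees of freedom cannot be relied on because the information matrix is singular.
- The fit is reported as not converged. The ladder can then end at equal variances for Weeks 14 and 26, with a Week 26 SE about 1.26 to 0.86 times the unstructured one for variance ratios of 0.5 to 2. There is no loss if the variances are equal. These ratios and the correlation of 0.5 are assumptions.

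The point is minor. It is confined to the exploratory addendum of about 40 completers, including the other CGM objectives where they reuse the model. The HbA1c analysis in SAP 5.9 is not affected.

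**What to change.** Delete the sentence on the random subject effect from SAP 7.4. Alternatively, replace it with a statement that subject identifies the repeated measurements and that no random effect is fitted alongside a residual covariance structure. Either brings the addendum into line with SAP 5.9: unstructured then has 3 parameters for 3 moments, all eight structures are identified, and the ladder responds only to real convergence problems.

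The cost is one sentence, with no change to data, sample size or fixed effects. One side effect should be known: without the random effect, Variance Components treats Weeks 14 and 26 as uncorrelated, as it already does in SAP 5.9. It would be reached only after seven identified structures had failed.
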